#### **14.3.3 OL Matching Inclusion/Exclusion for NH**

Subjects from the NH were selected to reflect the baseline criterion of the CPI-IFE007 study before the propensity score is calculated. The following criteria were applied for matching with the OL subjects:

- Male subjects  $\geq 7$  years old.
- 2 years data of LVEF
- Baseline value LVEF of  $\geq 35\%$  (baseline is month 12 in study)
- Subjects with no history of heart failure.
- No current treatment with givinostat (Duvyzyat®) (Variables: other\_meds\_listed ≠ “givinostat,” “duvyzyat”)
- Live subjects with non-missing cardiac efficacy data (CFB LVEF and CFB Myocardial strain) at baseline and month 12 for OL. Live subjects with non-missing cardiac efficacy data (LVEF and Myocardial strain) at month 12 and month 24 for OL. Missing data will not be imputed.

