The total duration of the study participation for each subject is up to 52 weeks. There is a repeatable optional open-label extension period where any subject completing 12 months of treatment is eligible to participate. Recruitment is planned to stop when approximately 48 subjects have completed 12 months of treatment. The end of the study is defined as the last subject's last visit/contact.

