7.3.1 Inclusion Criteria

Individuals who meet all of the following criteria are eligible for enrollment as study subjects:

1. Males 7 years of age and older with the diagnosis of DMD, defined as phenotype consistent with DMD and either positive genotype, first degree relative with positive genotype, or confirmatory muscle biopsy.
2. Stable dose of oral corticosteroids for at least 8 weeks or has not received corticosteroids for at least 30 days.
3. Stable cardiac function defined as change in LVEF of < 15% and no heart failure admission over the last 12 months; LVEF 35% or greater by cine CMR or echocardiography; myocardial damage in one or more left ventricular segments evident by late gadolinium enhancement allowed; concurrent angiotensin-converting enzyme inhibitors (ACEI), beta-blocker (BB) or angiotensin receptor blocker (ARB) therapy allowed (selection of which dictated by clinical care) if started three months or greater from first dose of IMP without change in dose. Aldosterone receptor antagonists (e.g. spironolactone or eplerenone) allowed if started 12 months or greater from first dose of IMP. No changes throughout the study allowed except in the event of a decline in left

ventricular ejection fraction (LVEF) >5% following the baseline CMR as measured by a subsequent CMR at the same center. Should this occur, changes in cardiac medications are allowed on study, and the patient may remain on IMP.

- a. **Late-stage cohort:** Subjects are eligible for the late-stage cohort if the subject has:
 - i. LVEF 35%-45% by cine cardiac magnetic resonance imaging (MRI) or echocardiography or
 - ii. historically documented LVEF 35%-45% by cine cardiac magnetic resonance imaging (MRI) or echocardiography and if their baseline MRI is less than 50%.
4. Subjects aged 18 years and older, informed consent obtained directly. For subjects ages 7–17 years old (yo), both assent from the subject and permission from a parent or guardian.
5. AAV-based gene therapy permitted if ≥ 2 years from AAV administration and subject has documented cardiac decline defined as >5% decline in LVEF over a 2-year period following AAV administration using consecutive CMRs or echocardiography performed at the same center (must still meet inclusion criterion #3).

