7.3.2 Exclusion Criteria

Individuals who meet any of these criteria are not eligible for enrollment as study subjects:

1. Clinically significant illness other than DMD
2. Clinically significant laboratory abnormality not associated with DMD
3. Major surgery within six weeks prior to the first dose of study drug, or planned surgery during this study which would interfere with the ability to perform study procedures
4. Require antiarrhythmic therapy and/or initiation of diuretic therapy for management of acute heart failure in the last 6 months
5. A LVEF of < 35% by CMR and/or fractional shortening of < 15% based on (ECHO during screening
6. A known bleeding disorder or has received anticoagulant treatment within two weeks of study entry

7. Allergy to gadolinium contrast or known renal insufficiency defined as abnormal cystatin C or creatinine above the upper limit of normal for age. The male serum reference ranges as follows:
 - Age 7-9 years - 0.2 - 0.6 mg/dL
 - Age 10-11 years - 0.3 - 0.7 mg/dL
 - Age 12-13 years - 0.4 - 0.8 mg/dL
 - Age 14-15 years - 0.5 - 0.9 mg/dL
 - Age 16 years or older - 0.8 - 1.3 mg/dL
8. Non-MR compatible implants (e.g. neurostimulator, automatic implantable cardioverter-defibrillator [AICD])
9. Subjects who participated in a therapeutic clinical trial within 30 days or five half-lives (whichever is longer) of study entry
10. Any other condition that could interfere with the subject's participation

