8.1.3 Optional Open-Label Extension

Patients who complete 12 months of treatment are eligible to participate in a repeatable open-label extension period of 12 months. Should a subject elect to participate in the open-label extension, the transition from IMP to the open-label extension should be continuous. Patients who elect to participate in the open-label extension will complete the following additional procedures.

Month 15, 18 & 21 Phone Calls

- Inquire about AEs/Serious Adverse Events (SAEs) and IMP tolerability
- Record all medication use with start date and dose; check for prohibited medications
- Confirm compliance (subject diary & pill counting) & dietary requirement

- Remind subject to complete and return at-home PedsQL, GI module & NMM (**Month 18 only**)

Should the subject report a new or worsening symptom, additional safety phone calls and/or safety visits may be scheduled at the investigator's discretion and safety labs performed. Any new or worsening abnormal lab should be followed and repeated until back to baseline or resolved.

Month 18 At-home Quality-of-Life surveys

- Complete and return Month 18 at-home PedsQL, GI module & NMM

Month 24 Treatment Visit

After 12 additional months of treatment, subjects will return to the site for Month 24 Treatment Visit.

- Record all medication use with start date and dose; check for prohibited medications.
- Inquire about AEs/Serious Adverse Events (SAEs) and IMP tolerability.
- Confirm compliance (subject diary & pill counting) & dietary requirement.
- Perform ECG, a physical exam with vital signs (blood pressure, heart rate, respiration rate, body temperature, weight).
- Obtain blood samples for clinical laboratory tests:
 - Complete Blood Count with differential: must include hemoglobin, hematocrit, platelet count, total white blood cell count with five-part differential count, and total red blood cell count.
 - Comprehensive Metabolic Panel: must include serum creatinine, blood urea nitrogen, glucose, total protein, albumin, total bilirubin, alanine aminotransferase, aspartate aminotransferase, alkaline phosphatase, electrolytes (sodium, potassium, chloride), calcium, bicarbonate, and creatine phosphokinase.
 - Coagulation Factors: prothrombin time reported as the international normalized ratio (INR) value (PT-INR), partial thromboplastin time (PTT or aPTT).
- Collect urine and blood samples for eicosanoid metabolites and other biomarkers.
- Month 24 CMR (\pm 7 day window)

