#### **4.5.2 Matching Algorithm**

For the DB period, NHS subjects will be matched to high-dose ifetroban subjects at a 2:1 ratio using a global optimal algorithm based on the nearest neighbor approach without replacement and without caliper. For the open-label period, NHS subjects will be matched to all open-label subjects at a 2:1 ratio using the same methodology.

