### 14.3.2 DB Inclusion/Exclusion for NH

Subjects from the NH were selected to reflect the baseline criterion of the CPI-IFE007 study before the propensity score is calculated. The following criteria will be applied for matching with the DB subjects given the High dose:

- Male subjects  $\geq$  7 years old.

- 2 years data of LVEF.
- Baseline value LVEF of  $\geq 35\%$  (baseline is pre-dose in study)
- No current treatment with givinostat (Duvyzyat®), empagliflozin (Jardiance®), dapagliflozin (Farxiga®), canagliflozin (Invokana®) (Variables: other\_meds\_listed ≠ “givinostat,” “emplagliflozin,” “dapagliflozin,” “canaglifloxin,” “duvyzyat,” “Jardiance,” “farxiga,” “Invokana”)
- Corticosteroids Stable Dose (Stable dose for  $\geq 56$  of corticosteroids days or no corticosteroids for  $< 30$  days prior to the start of baseline).
- Subjects with no history of heart failure.
- Live subjects with non-missing cardiac efficacy data (CFB LVEF and CFB Myocardial strain) at baseline and month 12
- Patients given High dose in DB

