#### **14.3.6 Analysis Population**

For the DB period, only high dose active and placebo subjects with Month 12 evaluable cardiac efficacy data will be included in the analysis.

For OL, all ifetroban treated subjects in the ITT population will be matched with natural history data.

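### The 35% LVEF floor for open-label natural-history controls is set at Month 12 for controls only, so an open-label subject below 35% has no comparable control

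*SAP*

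**What the plan says.** **Controls.** SAP 14.3.3 says the NHS patients for the OL match are chosen to mirror the trial's baseline criterion, before the propensity score is calculated. It then sets LVEF at 35% or more, with the note "baseline is month 12 in study". The double-blind list in SAP 14.3.2 has the same floor with the note "baseline is pre-dose in study".

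**Trial subjects.** The trial's own floor is a screening criterion (Protocol 7.3.2): "A LVEF of < 35% by CMR and/or fractional shortening of < 15% based on" echocardiography. After a fall in LVEF on study, Protocol 7.3.1 says: "Should this occur, changes in cardiac medications are allowed on study, and the patient may remain on IMP". Extension entry depends only on completing treatment. Protocol 8.1.3: "Patients who complete 12 months of treatment are eligible to participate in a repeatable open-label extension period of 12 months". Protocol 7.1: "any subject completing 12 months of treatment is eligible to participate".

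**The match.** SAP 14.3.6: "For OL, all ifetroban treated subjects in the ITT population will be matched with natural history data". SAP 4.5.2 matches 2:1, "using a global optimal algorithm based on the nearest neighbor approach without replacement and without caliper". SAP 14.3.4 makes Month 12 LVEF a propensity covariate for the OL period.

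**The comparisons.** SAP 14.3.7 lists two sets of tables under the OL study: Month 12 to 24 (all OL and subgroups against NH) and Baseline to Month 24 (High to High against NH).

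**The concern.** The two sides of the OL comparison pass through different filters. A trial subject whose LVEF has dropped below 35% by Month 12 stays in. An NHS patient with the same Month 12 value is barred. The propensity model cannot repair this, because the bar is applied before the score is fitted. Without a caliper, the subject is still paired with two controls at or above 35%.

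The subjects most exposed are the advanced cohort, who enter at 35-45%, or below 50% with a historical value of 35-45%. The protocol synopsis makes the NHS the primary comparator for the extension, so a fault in forming that group bears directly on the long-term efficacy reading. The two comparisons can also be pushed in opposite directions, so that one-year and two-year results appear to conflict when nothing real differs.

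**Working it through.** The plan gives no figure to reproduce. The check is to locate where the floor acts in each comparison, then to size the effect with no drug effect and the same natural history in both groups.

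**Step 1. Where the floor acts.**
- Month 12 to 24: Month 12 is the declared baseline of the OL match and a matching covariate. The floor acts at baseline. The fault is missing overlap below 35%.
- Baseline to Month 24: a Month 12 value is a post-baseline outcome. If the 14.3.3 controls are used, NHS patients who fell below 35% in year one are removed, while High-to-High subjects who did so are kept.

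**Step 2. Formula.** Let p be the share of trial subjects below 35% at Month 12 and D the LVEF change. Comparing all trial subjects with controls cut at 35%, before matching:

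bias = E[D] - E[D | at least 35%] = p x (E[D | below 35%] - E[D | at least 35%])

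Example (decline 2 points a year, SD of true yearly change 4, measurement SD 4): p = 0.140.
- Month 12 to 24: bias +0.48, so those below 35% changed 0.48/0.140 = 3.4 points more favourably than the rest (regression to the mean).
- Baseline to Month 24: bias -0.65, so they changed 0.65/0.140 = 4.6 points less favourably.

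If p = 0, both are zero. If yearly changes are a pure random walk without measurement error, the Month 12 to 24 bracket is zero.

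**Step 3. Simulation of the matched analysis.** None of these inputs is in the documents:
- half early and half advanced subjects; true entry LVEF normal with mean 56, SD 6 (early) or mean 42, SD 5 (advanced), kept if the observed entry value is above 45 or within 35-45 respectively;
- independent yearly true changes plus measurement error at each visit;
- 36 OL subjects (12 High to High) and a pool of 150 NHS patients;
- 2:1 optimal matching without caliper on LVEF alone, in place of the full propensity score; 400 runs per row.

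Bias is trial change minus NHS change in LVEF points; positive favours ifetroban.

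| Yearly decline | SD true change | SD measurement | Below 35% at Month 12: all / advanced | Month 12-24, matched on Month 12 LVEF | Baseline-24, matched on Month 12 LVEF | Baseline-24, matched on pre-dose LVEF |
|---|---|---|---|---|---|---|
| 1 | 2 | 2 | 6.4% / 12.8% | +0.06 | -0.12 | -0.18 |
| 1 | 4 | 2 | 9.5% / 19.0% | -0.04 | -0.47 | -0.92 |
| 1 | 4 | 4 | 11.5% / 22.7% | +0.17 | -0.34 | -0.64 |
| 2 | 2 | 2 | 9.3% / 18.6% | +0.13 | -0.12 | -0.33 |
| 2 | 4 | 2 | 12.3% / 24.4% | +0.12 | -0.37 | -0.91 |
| 2 | 4 | 4 | 14.0% / 27.4% | +0.28 | -0.44 | -0.90 |
| 4 | 2 | 2 | 16.9% / 33.7% | +0.13 | -0.31 | -0.58 |
| 4 | 4 | 2 | 18.9% / 37.4% | +0.19 | -0.69 | -1.11 |
| 4 | 4 | 4 | 19.7% / 38.2% | +0.51 | -0.70 | -1.22 |

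Simulation standard errors are 0.03 to 0.07 for Month 12-24 and 0.04 to 0.14 for Baseline-24. The last column uses the 12 High-to-High subjects; the other two bias columns use all 36.

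**Step 4. Remove the floor at Month 12.** On the same simulated subjects, the bias becomes -0.09 to +0.13 for Month 12-24 and -0.23 to +0.17 for Baseline-24 (matched on pre-dose LVEF), about zero within simulation error. In the row with the single negative Month 12-24 value, the no-floor result is -0.09, so the floor itself adds -0.04 - (-0.09) = +0.05. In the last row it adds 0.51 - 0.13 = +0.38.

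**The case against.** A reader might infer that both OL comparisons are biased because the controls are truncated after baseline. The documents do not support that. For Month 12 to 24 the floor sits at the declared baseline, and matching on Month 12 LVEF removes part of the imbalance. What remains is small, and is zero under either condition in Step 2.

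For Baseline to Month 24, neither SAP 6.4.1 nor 14.3.7 names the control set. The double-blind match is also made to high-dose subjects, with the floor at pre-dose. If that set serves the two-year comparison, this bias does not arise. The analysis diagram (SAP Figure 2) is not in the text available and may settle it. The OL set is the more natural reading: the two-year tables are listed under the OL study, SAP 14.3.1 describes only a double-blind and an OL match, and only 14.3.3 expressly asks for cardiac data at Month 24. That is inference, so the point stays conditional.

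A reader might also infer an effect of one to two points or more. Sizes of that order come mainly from advanced-stage subjects alone and from unmatched contrasts. The plan matches, and half its sample is early stage. The documents give no progression rate or SD, so even the presence of OL subjects below 35% is an expectation, not a stated fact.

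SAP 14.3.8 offers only partial protection. The weighting analysis is limited to the double-blind period. The caliper and exact-matching analyses name no period. The whole-cohort analysis uses the eligible NHS cohort, which would keep the floor. SAP 4.5.3 labels the NHS comparisons supplementary and the primary endpoint is safety. This limits the consequence without correcting the rule.

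**Conclusion.** The rule is wrong as written. It claims to mirror the trial's baseline criterion but applies at Month 12 a floor that trial subjects face only at screening.

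- **Month 12 to 24:** missing overlap at baseline, worth -0.04 to +0.51 LVEF points after matching, mostly favouring ifetroban.
- **Baseline to Month 24:** if the 14.3.3 controls are used, selection on a post-baseline value, worth 0.12 to 1.22 points against ifetroban.

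The one-sidedness is established by the text. The sizes depend on the assumed trajectories, pool size and LVEF-only match, and the second also depends on which control set is meant.

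**What to change.** 1. In SAP 14.3.3, apply the 35% floor at the NHS visit corresponding to trial baseline, with no floor at the Month 12 index visit. Keep Month 12 LVEF as a propensity covariate for Month 12 to 24.
2. In SAP 6.4.1 and 14.3.7, state that the Baseline-to-Month 24 controls are matched on pre-treatment values, with the floor at that visit.
3. Report how many OL subjects are below 35% at Month 12.
4. Reconcile SAP 4.4.1, which defines OL baseline as the last value at or before the start of ifetroban, with 14.3.3 and 14.3.4, which use Month 12. For subjects on ifetroban in the double-blind period these are different visits.

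Applying the Month 12 floor to both groups would also remove the Month 12 to 24 bias (-0.12 to +0.12 in the simulation). However, it discards trial subjects and would make the two-year comparison select both groups on an on-treatment value.

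Cost: SAP wording and a re-run of the OL match. Section 14.3.3 already asks for NHS data at baseline, so no new data are needed. A few NHS patients below 35% at the index visit would be admitted.

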#### **14.3.4 List of Baseline Covariates for Modeling**

The following baseline covariates will be included in the DB and OL Model to create the propensity score.

- Age
- Baseline left ventricular ejection fraction (LVEF). Baseline will represent pre-treatment values in DB and Month 12 visit values will be the baseline in the OL study.
- Background DMD medications (current steroids, Current ASO/exon skipping)
- Additional cardiac medications (Aldosterone antagonists, Beta-blocker, ACEi, ARB, Calcium channel blockers, ARNI)

The following chart will be used to define the baseline med covariates in the NH dataset.

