11.5 Historical Comparator

Data collected from an FDA-funded DMD NHS will be used as a historical comparator/supplemental placebo group ([Soslow 2023](#)). The NHS utilized as a comparator is an ongoing, multi-year, multicenter study evaluating the natural progression of DMD. Eligibility is broad based on DMD diagnosis, and endpoints collected mirror endpoints collected for CPI-IFE-007 except patient-reported outcomes (PedsQL). NHS visits are scheduled yearly, and demographic, baseline characteristics, medical history, and concomitant medication information is collected at each visit along with CMR, PFTs, QMT, and accelerometry. Patients from the NHS will be selected at a 2:1 ratio (NHS to placebo) using propensity score matching (PSM) based on baselined LVEF, age, and background DMD therapy with consideration for other relevant cardiac medications (ACEi, ARB, beta-blockers, ARNI, aldosterone receptor antagonists, diuretics, calcium channel blockers. Matched NHS patients will be added to the CPI-IFE-007 placebo group from the 12-month double-blind study to create a supplemental, representative placebo group of a larger size for Month 12 efficacy analyses. For the open label extension, a historical comparator group will be formed from NHS patients selected at a 2:1 ratio (NHS to open label high-dose ifetroban) using PSM as described above. The NHS comparator group for the open label extension will be compared with open-label high-dose ifetroban patients at Month 12, Month 24, and Month 36.

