#### **4.5.1 Propensity Score Matching Methodology**

Propensity scores will be calculated separately for the DB and open-label periods using logistic regression models with treatment assignment as the dependent variable. The independent variables will include: age, baseline LVEF, background DMD medications (steroids, ASO/exon-skipping therapy), and cardiac medications (ACEi, ARB, ARNI, beta-blocker, calcium channel blocker, aldosterone receptor antagonist, diuretic) as defined in [Section 14.3.4](#).

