## 5.2 Demographics and Baseline Characteristics

Demographic and baseline characteristics will be summarized by treatment group and overall.

Continuous demographic variables include age [years] at the time of informed consent, weight (kg), BMI (kg/m^2), and BMI z-scores.

Categorical demographic variables include BMI group (Underweight (<18.5), Normal weight (18.5-24.9), Overweight (25.0-29.9), and Obese ≥30), gender, race, ethnicity.

Categorical baseline characteristics variables are ambulatory (Yes/No), ventilatory support (Yes/No), stage of DMD (Late (35%-45%); Early (>45%)), Background DMD therapy (steroid alone, steroid + ASO (Exon-skipping therapy) ASO alone, none), and other cardiac medications (ACEi; ARB; ARNI; beta-blocker; diuretic; Aldosterone receptor antagonist; calcium channel blocker—outlined in the concomitant medication CRF; see [Table 1](#) below for complete listing of drugs in each class). Mutational analysis results will be included with age of DMD diagnosis.

Summary statistics for continuous variables will be presented as mean, standard deviation, minimum, median, and maximum, and for categorical variables, frequency counts and percentages.

A subject-data listing of demographics will be provided.

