## 6.5 Subgroup Analyses

To assess the consistency of treatment effects across the subgroup levels, and to examine baseline biomarkers for their potential value to predict treatment response, exploratory subgroup analyses will be conducted for safety, tolerability, pharmacokinetics, and efficacy for the variables below.

The following subgroups will be assessed using the primary endpoint and primary endpoint related to clinical assessments, secondary endpoints, and exploratory endpoints.

- DMD disease stage (Early LVEF>45%, Late LVEF 35%-45%)
- Ambulation status (ambulatory vs non-ambulatory)
- Background therapy (none, steroids, ASO, steroids + ASO)

For each subgroup analysis, results will be presented as stratified analyses with descriptive statistics and treatment effect estimates within each subgroup level. Forest plots will be used to display treatment effects across subgroup levels for key endpoints. No formal statistical testing for interaction between subgroup and treatment will be performed due to limited sample sizes within subgroups, but the consistency of treatment effects across subgroup levels will be evaluated qualitatively. These analyses are considered exploratory and intended to identify potential patterns that may inform future research rather than to draw definitive conclusions about differential treatment effects.

Missing data in each factor, which will be limited if any, will not be included (as a separate group) in subgroup analyses. This does not apply to the PSM analysis.

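### Natural history matching ignores AAV gene therapy, although inclusion 5 admits recipients only after their LVEF has fallen

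*SAP*

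**What the plan says.** **Entry rule.** Protocol 7.3.1, criterion 5: "AAV-based gene therapy permitted if ≥ 2 years from AAV administration and subject has documented cardiac decline defined as >5% decline in LVEF". The decline must occur over a 2-year period after AAV, and the subject must still meet criterion 3 on stable cardiac function.

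**Matching rule.** Protocol 11.5 selects NHS patients "using propensity score matching (PSM) based on baselined LVEF, age, and background DMD therapy", with consideration of cardiac medications. Under Historical Comparator Analyses, the protocol synopsis makes the NHS a supplement to placebo in the double-blind period and the primary comparator in the open-label extension.

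**How the SAP carries this out.** Section 3 says the SAP follows protocol Amendment 04a. Section 4.4.4 says the protocol-specified analyses are unchanged. Background therapy is then defined as follows:

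- Propensity model, 4.5.1: "background DMD medications (steroids, ASO/exon-skipping therapy"); 14.3.4: "Background DMD medications (current steroids, Current ASO/exon skipping"). Table 1 lists drug classes and NHS variable names, with none for AAV.
- Baseline table, 5.2: "Background DMD therapy (steroid alone, steroid + ASO (Exon-skipping therapy) ASO alone, none").
- Subgroups, 6.5: "Background therapy (none, steroids, ASO, steroids + ASO").
- NHS selection, double-blind, 14.3.2: "No current treatment with givinostat (Duvyzyat®), empagliflozin (Jardiance®), dapagliflozin (Farxiga®), canagliflozin (Invokana"). For the open-label period, 14.3.3 keeps only the givinostat exclusion. Neither list mentions AAV.

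**The concern.** AAV recipients enter the trial partly because their LVEF has been falling, and LVEF change is the main efficacy measure. Matching on baseline LVEF equalises the level but not the preceding slope. Of two patients at the same LVEF, one required to have been declining and one not, the expected next-year change may differ. It could be steeper (selected decliners) or flatter (an effect of the gene therapy, or regression after selection).

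The NHS rules apply no counterpart to inclusion 5. An NHS patient with recent AAV, or with AAV and no decline, could be a control although the trial would not admit him. Any resulting difference would be read as an ifetroban effect or would mask one. This matters most in the open-label period, where no concurrent randomised control remains.

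**Working it through.** The plan gives no figure on this point to reproduce. The check is a comparison of the texts, followed by an illustration of size.

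**Step 1: could other SAP text capture AAV?**

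- The medication covariates in 14.3.4 are current treatments. A single administration at least 2 years earlier does not fit.
- Concomitant medications in SAP 5.5 are those given after treatment starts, so prior AAV falls outside.
- Prior LVEF slope is not a covariate. The NHS rules ask for two years of LVEF data but require no decline.
- The sensitivity analyses in 14.3.8 (weighting, caliper 0.2, exact matching, whole-cohort adjustment) do not name AAV. Exact matching is left to unspecified categorical variables.
- On the trial side the information should exist: protocol 8.1.1 records all background DMD therapy at screening. The documents do not say whether the NHS records AAV or contains recipients.

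**Step 2: size in the double-blind NHS comparison.**

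From the documents: 16 high-dose and 16 placebo subjects (8 early plus 8 advanced per arm, protocol Table 7-1). A 2:1 ratio gives 32 NHS subjects, so the pooled control has 16 + 32 = 48.

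Assumed: k = 1 to 3 AAV recipients in each randomised arm, none in the NHS, and annual LVEF change differing by d = 1 to 3 points between recipients and others.

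Shift = k·d/16 − k·d/48 = k·d/24.

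- k = 1, d = 1: 1/24 = 0.04 points
- k = 3, d = 3: 9/24 = 0.38 points

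SAP 14.3.1 also gives the ratio as 2:1 placebo to high dose. If that means 32 controls in total, the shift is k·d/16 − k·d/32 = k·d/32, or 0.03 to 0.28 points.

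**Step 3: open-label comparison.** SAP 14.3.6 matches all ifetroban-treated subjects to the NHS, and no placebo subjects sit in the comparator to offset the difference. With the same AAV share and all other assumptions kept, the one-year shift is k·d/16: 1/16 = 0.06 to 9/16 = 0.56 points.

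**Step 4: effect on the test.** The planned test is the Wilcoxon rank sum test. With no true effect, 16 high-dose against 16 placebo plus 32 NHS, k recipients in each randomised arm and an extra decline of d SD each, 20,000 simulated trials per row gave:

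| k | d (SD) | Mean shift (SD) | Two-sided rejection at 0.05 |
|---|---|---|---|
| 1 | 0.5 | 0.02 | 0.050 |
| 2 | 1.0 | 0.08 | 0.046 |
| 4 | 0.5 | 0.08 | 0.056 |
| 4 | 1.0 | 0.17 | 0.067 |

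With k = 0 the rate was 0.047 to 0.051. One or two recipients barely move it; four begin to. The shift here runs against ifetroban only because extra decline was assumed.

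**The case against.** **Readings the documents do not support.**

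- A reader might infer that AAV recipients are matched to controls who never had gene therapy. Nothing says so. Protocol 11.5 describes NHS eligibility as broad, and the selection rules neither exclude nor require AAV.
- A reader might infer that AAV recipients all land in the none or steroids levels. Protocol 7.4 permits ASO and nothing bars it after AAV, so they could fall in any of the four levels.
- Nor are they misclassified. The levels describe steroid and ASO use, and an AAV recipient on steroids belongs in steroids. The fault is that the level mixes two kinds of patient.
- The entry rule implies 5/2 = 2.5 points a year if the 5% is absolute. That is a past within-subject decline, not a difference from controls, who may also decline. It does not fix d.

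**The case for leaving the plan alone.** Protocol 11.5 does not define background DMD therapy, and inclusion 5 only permits AAV without calling it that. Current medications are a narrow but possible reading. The number of recipients may be zero. The primary endpoint is the percentage of subjects with TEAEs, the subgroups are exploratory, and SAP 4.5.3 labels the NHS comparisons supplementary. The randomised comparison is unbiased in expectation.

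**What stands.** These points limit size and scope; they do not close the gap. Whatever the term means, inclusion 5 selects on the outcome's own trajectory and nothing in the NHS matching reflects that. The supplementary label does not displace the protocol's use of the NHS as primary comparator in the extension.

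A further objection is correct: adding AAV to the propensity model as well as matching on it would be redundant. Section 14.3.4 already lists ten covariates for about 16 high-dose subjects, and an AAV term may not be estimable.

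**Conclusion.** The omission is real and confined to the NHS comparisons and the baseline and subgroup displays. As written, the SAP matches controls without regard to AAV status or prior LVEF decline, in an analysis the protocol describes as matched on background DMD therapy. The double-blind shift of about 0.04 to 0.38 LVEF points rests wholly on the assumptions in step 2, of which k, d and the absence of AAV in the NHS have no source in the documents. The open-label comparison is more exposed because no randomised placebo subjects dilute the difference. Direction cannot be predicted, which is a reason to settle the handling before results are seen. It should be corrected, but it does not threaten the randomised LVEF comparison in expectation.

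**What to change.** 1. Derive prior AAV gene therapy (yes/no) for trial subjects. Report it per arm in SAP 5.2 and give it its own level in 6.5.
2. In 14.3.2 and 14.3.3, match exactly on AAV status, using only NHS recipients who can be shown to meet inclusion 5. Do not also add AAV to the propensity model.
3. If the NHS does not record AAV or has no eligible recipient, remove AAV-treated trial subjects, including those on placebo, from the NHS comparisons only. Keep them in the randomised comparison. If AAV is unrecorded in the NHS, state that treated controls cannot be ruled out.

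The trial-side cost is one derived variable and a few lines of SAP text. Showing that NHS recipients meet inclusion 5 takes more: AAV dates and serial LVEF after AAV. The downside is the loss of a few subjects from the NHS comparisons.
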